### Subgroup Analysis

Safety, efficacy and immunogenicity endpoints may be analyzed in select subgroups specified below as applicable:

- Baseline SARS-CoV-2 Status (Positive, Negative)
- Pre-booster/third dose SARS-CoV-2 Status (Positive, Negative)
- Age (6 Months to < 2 Years, 2 Years to < 6 Years, and 6 Years to < 12 Years)
- Sex (Female, Male)

- Race
- Ethnicity
- Obesity status (Obesity is defined as BMI  $\geq 95^{\text{th}}$  percentile for age based on WHO growth reference data)

All analyses and data summaries/displays will be provided by vaccination group for each age group (6 months to  $< 2$  years, 2 years to  $< 6$  years, and 6 years to  $< 12$  years), unless otherwise specified.

All analyses will be conducted using SAS Version 9.4 or higher.

## 6.2. Background Characteristics

### 6.2.1. Subject Disposition

The number and percentage of subjects in the following categories will be summarized by age and vaccination group as defined in [Section 6.1](#) based on specific analysis datasets for Part 2 Open-label Phase, and Booster Dose Analysis separately:

For mRNA-1273 Primary Series Long-term and mRNA-1273 Booster:

- Full Analysis Set (Long-term Analysis)
- Full Analysis Set (Booster Dose Analysis)
- Immunogenicity Subset (Long-term Analysis)
- Immunogenicity Subset (Booster Dose Analysis)
- PP Immunogenicity Subset (Long-term Analysis)
- PP Immunogenicity Subset (Booster Dose Analysis)
- PP Immunogenicity Subset - Pre-booster SARS-CoV-2 Negative (Booster Dose Analysis)
- mITT1 Set (Long-term Analysis)
- mITT1 Set (Booster Dose Analysis)
- Solicited Safety Set (Booster Dose Analysis)
- Safety Set (Long-term Analysis)

- Safety Set (Booster Dose Analysis)

For mRNA-1273.214 Booster:

- Full Analysis Set (Booster Dose Analysis)
- Safety Set (Booster Dose Analysis)

For Part 3 First Two Doses of Primary Series, and Third Dose Analysis separately:

- Full Analysis Set
- Full Analysis Set (Third Dose Analysis)
- Solicited Safety Set
- Solicited Safety Set (Third Dose Analysis)
- Safety Set
- Safety Set (Third Dose Analysis)
- Immunogenicity Subset
- Immunogenicity Subset (Third Dose Analysis)
- PP Immunogenicity Subset
- PP Immunogenicity Subset (Third Dose Analysis)

The percentage will be based on subjects in that age and vaccination group within the Full Analysis Set for long-term analysis and booster/third dose analysis separately, except the Solicited Safety Set and Safety Set for which the percentages will be based on the age and vaccination group in the Safety Set (as treated) for long-term analysis and booster/third dose separately.

The number and percentage of subjects in each of the following disposition categories will be summarized by age and vaccination group based on the Randomization Set in Part 2:

- Received each dose of IP in Part 2 blinded phase
- Continuing and unblinded in Part 2 open-label phase
- Received each cross-over dose of IP in Part 2 open-label phase
- Prematurely discontinued study vaccine during Part 2 open-label phase and the reason for discontinuation

- Received mRNA-1273 booster dose in booster dose analysis for Part 2
- Received mRNA-1273.214 booster dose in booster dose analysis for Part 2
- Completed study
- Prematurely discontinued the study and the reason for discontinuation (for the entire study period, and for study parts in applicable subjects group)

The number and percentage of subjects in each of the following disposition categories will be summarized by age and vaccination group based on the Full Analysis Set for booster/third dose analysis:

- Received mRNA-1273 booster/third dose in booster/third dose analysis
- Received mRNA-1273.214 booster dose in booster dose analysis
- Completed study
- Prematurely discontinued the study and the reason for discontinuation

A subject disposition listing will be provided, including informed consent date, subjects who completed the study injection schedule, subjects who completed study, subjects who discontinued from study vaccine or who discontinued from participation in the study, with reasons for discontinuation.

A subject from Part 1 or Part 2 who completed 12 months of follow up after the last injection received is considered to have completed the study if not received booster dose. For subject who completed 12 months of follow up after the booster injection received is considered to have completed the study if received booster dose. For Part 3 subjects who completed 12 months of follow up after the third injection received is considered to have completed the study.

### **6.2.2. Demographics**

Descriptive statistics will be calculated for the following continuous demographic and baseline characteristics: age (years), weight (kg, z-score), height (cm, z-score), and body mass index (BMI) (kg/m^2, z-score). Number and percentage of subjects will be provided for categorical variables such as gender, race, ethnicity. The summaries will be presented by age and vaccination group as defined in [Section 6.1](#) if applicable, based on the Safety Set, FAS, mITT1 Set, Immunogenicity Subset, and PP Immunogenicity Subset (by pre-booster/third dose SARS-CoV-2 status and overall for booster/third dose analysis).

### **6.2.3. Medical History**

Medical history data will be coded by system organ class (SOC) and preferred term (PT) using the Medical Dictionary for Regulatory Activities (MedDRA).

The number and percentage of participants with any medical history will be summarized by SOC and PT based on the Safety Set. A participant will be counted only once for multiple events within each SOC and PT. SOC will be displayed in internationally agreed order. PT will be displayed in descending order of frequency and then alphabetically within SOC.

Medical history data will be presented in a listing.

Medical history data for participants who entered study in Part 1 open-label phase or Part 2 blinded phase will be provided in Part 1 open-label phase and Part 2 blinded Phased analysis.

### **6.2.4. Prior and Concomitant Medications**

Prior and concomitant medications and non-study vaccination will be coded using the World Health Organization (WHO) drug dictionary (WHODD). The summary of concomitant medications will be based on the Safety Set (Booster/Third Dose Analysis). Categorization of prior, concomitant, and post medications is summarized in [Appendix C](#) Table 5.

The number and percentage of subjects using concomitant medications and non-study vaccination during the 7-day follow-up period (i.e., on the day of injection and the 6 subsequent days) and during the 28-day follow-up period after booster/third dose injection in booster/third dose analysis (i.e., on the day of injection and the 27 subsequent days) will be summarized by vaccination groups as defined in [Section 6.1](#) as follows:

- Any concomitant medications and non-study vaccination within 7 Days Post Injection
- Any concomitant medications and non-study vaccination within 28 Days Post Injection
- Seasonal influenza vaccine within 28 Days Post Injection
- Antipyretic or analgesic medication within 28 Days Post Injection

A summary table of concomitant medications and non-study vaccination that continued or newly received at or after the first injection through 28 days after the booster/third injection will be provided by PT in descending frequency in the mRNA-1273 group.

Medications taken to prevent pain or fever will be collected on eDiary and summaries will be provided based on the Solicited Safety Set by vaccination group as defined in [Section 6.1](#) for booster/third injection, including within 7 days after injection, beyond 7 days after injection.

Concomitant and post medications and non-study vaccination will be presented in a listing.

#### **6.2.5. Study Exposure**

Study IP administration data will be presented in a listing for Part 2 open-label phase and booster dose analysis and Part 3 third dose analysis separately.

Long-term analysis study duration will be summarized as earliest date of (study discontinuation, study completion, death, and data cutoff date) - first dose of mRNA-1273 + 1.

Booster/Third dose analysis study duration will be summarized as earliest date of (study discontinuation, study completion, death, and data cutoff date) – date of booster/third injection +1.

#### **6.2.6. Major Protocol Deviations**

Major protocol deviations are a subset of protocol deviations that may significantly impact the completeness, accuracy, or reliability of the study data or that may significantly affect a subject's rights, safety, or well-being. Major protocol deviations rules will be developed and finalized before database lock.

The number and percentage of the subjects with each major protocol deviation type will be provided by age and vaccination group as defined in [Section 6.1](#) based on the FAS (Booster/Third Dose Analysis).

Major protocol deviations will be presented in a listing.

### **6.3. Safety Analysis**

Safety and reactogenicity will be assessed by clinical review of all relevant parameters including solicited ARs (local and systemic), unsolicited AEs, SAEs, MAAEs, AESI, AEs leading to withdrawal from study vaccine and/or study participation, and physical

examination findings. Unsolicited AEs will be coded by SOC and PT according to the MedDRA. Two modified versions of The Toxicity Grading Scale for Healthy Adult and Adolescent Volunteers Enrolled in Preventative Vaccine Clinical Trials (DHHS 2007) are used in this study for solicited ARs as presented in protocol section 7.4.3's Table 8 and 9; Table 8 is the pediatric toxicity scale used for children older than 36 months and < 12 years, and Table 9 is the infant/toddler toxicity scale used for children 6 to 36 months of age, inclusive.

All safety analyses will be based on the Safety Set, except summaries of solicited ARs which will be based on the Solicited Safety Set. All safety analyses will be provided by age and vaccination group unless otherwise specified.

### **6.3.1. Adverse Events**

A treatment-emergent AE (TEAE) is defined as any event occurring during the study not before exposure to study vaccine or any event already present that worsens after exposure to study vaccine. [Note: worsening of a pre-existing condition after vaccination will be reported as a new AE.]

Adverse events will also be evaluated by the investigator for the coexistence of MAAE which is defined as an AE that leads to an unscheduled visit to a healthcare practitioner.

Unsolicited AEs will be coded by PT and SOC using MedDRA and summarized by age and vaccination group, and stage (up to 28 days after any vaccination, follow-up analysis period and overall stage; see [Section 6.1](#) for definitions of vaccination group and stage).

All summary tables (except for the overall summary of AEs) for unsolicited AEs will be presented by SOC and PT for TEAEs with counts of subjects included. SOC will be displayed in internationally agreed order. PT will be displayed in descending order of frequency of total mRNA-1273 group with all dose level combined in Part 1 and in Part 2 correspondingly and then alphabetically within SOC. When summarizing the number and percentage of subjects with an event, subjects with multiple occurrences of the same AE or a continuing AE will be counted once. Subjects will be presented according to the highest severity (the strongest relationship) in the summaries by severity (of related AEs), if subjects reported multiple events under the same SOC and/or PT.

Percentages will be based upon the number of subjects in the Safety Set for specified analysis (long-term analysis or booster/third dose analysis) within each age and vaccination group.

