#### **3.3. Booster (Part 1 and Part 2)/Third Dose (Part 3)**

##### **3.3.1. Primary Safety Endpoints**

For mRNA-1273 Booster/Third Dose:

- Solicited local and systemic ARs through 7 days after booster or third dose
- Unsolicited AEs through 28 days after booster or third dose
- MAAEs through the entire study period after booster or third dose
- SAEs through the entire study period after booster or third dose
- AESIs through the entire study period after booster or third dose
- AEs leading to discontinuation from study participation after booster or third dose through the last day of study participation

For mRNA-1273.214 Booster Dose:

- MAAEs through the entire study period after booster dose
- SAEs through the entire study period after booster dose
- AESIs through the entire study period after booster dose
- AEs leading to discontinuation from study participation after booster dose through the last day of study participation

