### Booster/Third Dose Analysis

For unsolicited AE or assessments that will be collected throughout the study, this analysis period starts from the booster/third dose date and continues until the earliest date of (study completion, discontinuation from the study, or death).

**Unscheduled visits:** Unscheduled visit measurements will be included in analysis as follows:

- In scheduled visit windows per specified visit windowing rules.
- In the derivation of baseline/last on-treatment measurements.
- In the derivation of maximum/minimum on-treatment values and maximum/minimum change from baseline values for safety analyses.
- In individual subject data listings as appropriate.

**Visit windowing rules:** The analysis visit windows for protocol-defined visits are provided in [Appendix B](#).

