2. Refer to Protocol Section 6.1.1 for individual participant criteria for delay of study vaccination.
3. Pregnancy test prior to study injections on D1 and D29 will be a point-of-care urine test and will be performed if deemed appropriate by the investigator. At the discretion of the investigator, a pregnancy test either via blood or point-of-care urine test can be performed at any time during the study.

**8.6. Appendix F: Schedule of Assessments for Optional Booster Doses with mRNA-1273 for Parts 1 and 2, Study Arms 1 Through 9 under Protocol Amendment 7**

| Visit Number   | BD-1               | BD-2                       | BD-2A   | BD-3   |                                |                                | BD-4    | BD-5                          | BD-6    |
|--|--------------------|----------------------------|---|--------|--------------------------------|--------------------------------|---------|-------------------------------|---------|
| Type of Visit  | C                  | SC                         | C   | C      | SFU                            |                                | C       | SC                            | C       |
|  |                    |                            |   |        | eDiary                         | SC                             |         |                               |         |
| Study Visit Day   | BD-D1  | 7 days after BD-D1 (BD-D8) | 14 days after BD-D1 (Sub-Cohort E only and optional) BD-D15 | BD-D29 | Every 4 weeks BD-D43 – BD-D155 | Every 4 weeks BD-D57 – BD-D169 | BD-D181 | 270 days after BD-1 (BD-D271) | BD-D366 |
| Window Allowance (Days)   | 0                  | + 3                        | + 3   | -3/+14 | ± 3                            | ± 3                            | -3/+14  | + 3                           | -3/+14  |
| Days Since Most Recent Vaccination  | 0                  | 7                          | 14  | 28     |                                |                                | 180     | 270                           | 365     |
| Confirm informed consent /assent form booster addendum signing   | X                  |                            |   |        |                                |                                |         |                               |         |

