| Study Visit Day  | BD-D1  | 7 days after BD-D1 (BD-D8) | BD-D29 | Every 4 weeks BD-D57– BD-D169 | BD-D181 (EOS) |
| Window Allowance (Days)  | 0                  | + 3                        | -3/+14 | ± 3                           | -3/+14        |
| Days Since Most Recent Vaccination                             | 0                  | 7                          | 28     |                               | 180           |
| Confirm informed consent /assent form booster addendum signing | X                  |                            |        |                               |               |
| Physical examination                               | X                  |                            | X      |                               | X             |
| Pregnancy testing                                  | X                  |                            |        |                               |               |
| Immunogenicity Assessment                                      |                    |                            |        |                               |               |

| Visit Number   | BD-1               | BD-2                       | BD-3   | SFU                           | BD-4          |
|--|--------------------|----------------------------|--------|-------------------------------|---------------|
| Type of Visit  | C                  | SC                         | C      |                               | C             |
|  |                    |                            |        | SC                            |               |
| Study Visit Day  | BD-D1  | 7 days after BD-D1 (BD-D8) | BD-D29 | Every 4 weeks BD-D57– BD-D169 | BD-D181 (EOS) |
| Window Allowance (Days)  | 0                  | + 3                        | -3/+14 | ± 3                           | -3/+14        |
| Days Since Most Recent Vaccination   | 0                  | 7                          | 28     |                               | 180           |
| Pre-booster blood for immunologic analysis   | X                  |                            |        |                               |               |
| Dosing  |                    |                            |        |                               |               |

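### Entire-study MAAE, SAE, AESI and discontinuation percentages after booster rest on about 365 scheduled days for mRNA-1273 but 180 for mRNA-1273.214, and no person-time rate is planned

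*SAP*

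**What the plan says.** All references are to the booster SAP unless stated otherwise.

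- **Endpoints.** Section 3.3.1 lists the same open-ended endpoints for both products. For mRNA-1273.214 one reads "MAAEs through the entire study period after booster dose". SAEs and AESIs are worded alike, and AEs leading to discontinuation run to the last day of participation. For mRNA-1273.214 these four are the only primary safety endpoints.
- **Analysis period.** Section 6.1, on the booster/third dose analysis, states: "this analysis period starts from the booster/third dose date and continues until the earliest date of (study completion, discontinuation from the study, or death"). The period table in the same section adds data cutoff as an end point. No common truncation day is given.
- **Statistic.** Section 6.3.1: "Percentages will be based upon the number of subjects in the Safety Set for specified analysis (long-term analysis or booster/third dose analysis"), within age and vaccination group. Sections 6.3.1.1 and 6.3.1.2 plan counts and percentages of subjects only.
- **mRNA-1273 booster schedule (Appendix F).** eDiary safety follow-up is "Every 4 weeks BD-D43 – BD-D155" and safety calls are "Every 4 weeks BD-D57 – BD-D169". A further call falls "270 days after BD-1 (BD-D271") and the last visit is BD-D366. Appendix H also takes the Part 3 third dose to BD-D366.
- **mRNA-1273.214 schedule (Appendix J).** Calls only, "Every 4 weeks BD-D57– BD-D169". BD-D181 is marked as end of study.
- **Completion.** Section 6.2.1: "For subject who completed 12 months of follow up after the booster injection received is considered to have completed the study if received booster dose". No exception is made for mRNA-1273.214.

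**The concern.** A percentage of subjects with at least one event grows with the time each subject is watched. Section 6.1 lists the booster groups under one heading, and Section 6.3.1 asks for AE summaries by vaccination group. The entire-study figures for the two products are therefore likely to be read side by side, although one covers roughly twice the follow-up of the other and, over the shared months, more scheduled contacts. A lower mRNA-1273.214 percentage could then reflect a shorter window rather than fewer events per unit of time.

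**Working it through.** **1. Follow-up length.** The last scheduled visits are BD-D366 (Appendices F and H) and BD-D181 (Appendix J). With dosing on BD-D1, 366 − 1 = 365 days and 181 − 1 = 180 days. Both match the days-since-vaccination rows in the schedules. Ratio: 180/365 = 0.493.

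**2. Scheduled post-dose contacts to BD-D181.**

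| | Appendix F | Appendix J |
|---|---|---|
| BD-D8, BD-D29, BD-D181 | 3 | 3 |
| eDiary (BD-D43, 71, 99, 127, 155) | 5 | 0 |
| Calls (BD-D57, 85, 113, 141, 169) | 5 | 5 |
| Total | 13 | 8 |

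8/13 = 0.62. The optional BD-D15 visit of Sub-Cohort E is left out. Appendix F has MAAEs, SAEs and AESIs recorded at the eDiary contacts as well as the calls, so the extra five are real opportunities to capture events. Over the whole schedule, adding BD-D271 and BD-D366 to Appendix F, the count is 15 versus 8.

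**3. Effect of window length under identical risk.** The event rates are assumptions; the SAP gives none. With a constant hazard λ per person-year for both products, the expected percentage is 1 − exp(−λ × 180/365) for mRNA-1273.214 and 1 − exp(−λ) for mRNA-1273.

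| λ | 180 days | 365 days | Ratio |
|---|---|---|---|
| 0.02 | 1.0% | 2.0% | 0.50 |
| 0.1 | 4.8% | 9.5% | 0.51 |
| 0.5 | 21.9% | 39.3% | 0.56 |
| 1.0 | 38.9% | 63.2% | 0.62 |

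For very common events the ratio rises further: at an assumed 12-month risk of 90% it is 0.75.

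**4. Effect if events cluster after the dose.** For rare events, let a share f fall in the first 28 days and the rest spread evenly to day 365. The ratio is f + (1 − f) × (180 − 28)/(365 − 28) = f + (1 − f) × 152/337. This gives 0.59 for f = 25%, 0.73 for 50%, 0.86 for 75% and 1.00 for 100%.

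**5. What the stages in the plan cover.** Section 6.1 defines a stage covering the vaccination day and the next 27 days. It is the same length for both products, so window length does not distort it. Section 6.3.1 also names a follow-up stage and refers to Section 6.1 for it, but Section 6.1 of this SAP does not define one. Nothing beyond 28 days therefore provides a common window.

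**6. Result with the change.** Under the constant hazard of step 3, a common cut at BD-Day 181 or a rate per person-time returns a ratio of 1.00. Neither removes the 13 versus 8 difference in contacts.

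**7. Study completion.** Section 6.2.1 sets completion at 12 months after any booster, while Appendix J ends the mRNA-1273.214 schedule at BD-D181. Because the safety period ends at study completion, the two passages give that group different end dates.

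**The case against.** The strongest reply is that the SAP plans no comparison between the boosters. Each product is to be evaluated for safety, with endpoints listed under separate headings, and mRNA-1273.214 has no immunogenicity objective. The groups are not randomised. Under Amendment 7 the mRNA-1273 booster was offered to Part 1 children and to Part 2 children aged 6 to under 12 years; under Amendment 9 mRNA-1273.214 was offered to those still unboosted in all age groups (Section 4.1.3 of the SAP for the Part 1 open-label and Part 2 blinded phases). Equal windows would not make the contrast valid. The 28-day stage is the default primary safety period, and Section 6.2.5 summarises study duration, so a careful reader can see that follow-up differs.

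Most of this stands, and it limits the point to the entire-study summaries. It does not remove it. The 28-day period applies unless otherwise specified, and Section 3.3.1 specifies otherwise for these four endpoints. A duration summary shows that follow-up differs but does not correct the percentages.

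A reader might infer more than the documents support:

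- *That mRNA-1273.214 will look half as reactogenic.* Reactogenicity means solicited reactions on the injection day and the next 6 days. Section 6.3.2 rules out eDiaries after mRNA-1273.214, so follow-up length cannot halve that result.
- *That all booster safety percentages are distorted.* Window length does not affect the 28-day stage.
- *That the plan necessarily hides a two-fold excess.* That is the limit for rare events spread evenly over a year; steps 3 and 4 show smaller effects otherwise.
- *That mRNA-1273.214 has half the contacts.* The ratio of 5 to 10 holds only for the four-weekly contacts. To BD-D181 it is 8 to 13.

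**Conclusion.** The point holds for the open-ended endpoints of Section 3.3.1. Their percentages rest on about 365 versus 180 scheduled days, with fewer scheduled contacts for mRNA-1273.214 over the shared period, and no person-time rate is planned. From follow-up length alone, the mRNA-1273.214 percentage would be about 0.50 to 0.62 of the mRNA-1273 percentage at 0.02 to 1.0 events per person-year, and closer to 1 when events cluster soon after the dose. These ratios assume the same hazard for both products and full scheduled follow-up. The 180-day figure follows Appendix J and depends on how the conflict with Section 6.2.1 is resolved. The consequence is a risk of misreading descriptive tables, not an error in a planned test. It is worth correcting because the correction is cheap.

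**What to change.** In Section 6.3.1 of the booster SAP, for MAAEs, SAEs, AESIs and AEs leading to discontinuation:

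1. Add a summary for all booster and third-dose groups from the dose through BD-Day 181.
2. Add incidence per 100 person-years over all follow-up. Section 6.5.2 already uses person-time incidence with exact Poisson intervals for the efficacy endpoints.
3. Tabulate BD-Day 182-366 separately for the mRNA-1273 booster and the third dose.
4. Footnote the different contact schedules and state that the booster groups are not randomised.

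Separately, reconcile the completion rule in Section 6.2.1 with the end of study in Appendix J, so that the end of the safety period is unambiguous for mRNA-1273.214.

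Cost: SAP wording and a few extra displays. No new data are needed.
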